1. INTRODUCTION

Primary hyperoxaluria type 1 (PH1) is a rare autosomal recessive disease characterized by excessive oxalate production by the liver and consequent hyperoxaluria. PH1 is caused by mutations in the alanine glyoxylate aminotransferase (*AGXT*) gene, which encodes the liver peroxisomal enzyme alanine-glyoxylate aminotransferase (AGT). As a consequence of AGT deficiency, glyoxylate accumulates and is oxidized to oxalate in the hepatocyte and ultimately transported to the kidneys for excretion. Oxalate, in the form of its calcium salt, is excreted almost entirely by the kidney. Due to its insolubility, calcium oxalate can crystallize readily in the urinary tract. In PH1, excess urinary oxalate results in recurrent nephrolithiasis and/or nephrocalcinosis, which can lead to pain, infections, progressive kidney disease and failure, along with reduced quality of life.^[1] As renal function declines, elimination of oxalate is further reduced, such that calcium oxalate accumulates in bone, vasculature, skin, retina, heart, and nervous system, resulting in severe end-organ damage. This devastating condition, systemic oxalosis, arises when the estimated glomerular filtration rate (eGFR) has declined below 30 to 45 mL/min/1.73 m².

The analysis methods described in the protocol may be updated in this statistical analysis plan (SAP). Any changes to the data analysis methods described in the protocol, including justification for the changes, are described in Section 8 and in the clinical study report (CSR). Additional exploratory analyses of the data may be conducted when deemed appropriate.

2. STUDY OVERVIEW

2.1. Synopsis of Study Design

Study ALN-GO1-002 is an open-label, extension study designed to evaluate the long-term safety, pharmacokinetic (PK) and pharmacodynamics (PD) of subcutaneously administered lumasiran in patients with PH1 who completed the parent study (ALN-GO1-001). The number of patients may include up to 20 PH1 patients from Part B of Study ALN-GO1-001.

Eligible patients either receive the same dose and/or dose regimens of ALN-GO1 (hereinafter referred to as lumasiran) as administered in the parent study (1.0 mg/kg once monthly, 3.0 mg/kg once monthly or 3.0 mg/kg once every 3 months) or may change dose regimens at any time. Any change in dose regimen for a patient may occur due to emerging data and with the approval from the Safety Review Committee (SRC).

2.2. Study Procedures

The schedule of assessments is described in the study protocol (Table 1 and Table 2).

3. OBJECTIVES AND ENDPOINTS

3.1. Objectives

3.1.1. Primary Objective

- Evaluate the long-term safety of multiple doses of lumasiran in patients with PH1

3.1.2. Secondary Objectives

- Evaluate the PD effect of lumasiran on urinary oxalate excretion
- Characterize the effect of lumasiran on markers of renal function

3.1.3. Exploratory Objectives

- Characterize the PK of lumasiran
- Evaluate the PD effect of lumasiran on urinary glycolate, plasma oxalate concentration, plasma glycolate concentration and urine oxalate:creatinine ratio
- Characterize the quality of life
- Evaluate the incidence of anti-drug antibodies (ADA)

3.2. Endpoints

3.2.1. Primary Endpoint

- Incidence of adverse events (AEs)

3.2.2. Secondary Endpoints

- Change in urinary oxalate excretion over time
- Change in eGFR and measured creatinine clearance (mCrCl) over time

3.2.3. Exploratory Endpoints

- Describe the effect of lumasiran on other safety parameters, including assessments of vital signs, electrocardiograms (ECG), renal ultrasounds, clinical laboratory parameters, and physical examinations
- Assess lumasiran plasma PK parameters including maximum plasma concentration (C_{max}), time to maximum plasma concentration (t_{max}), elimination half-life, area under the curve, fraction of dose excreted in urine, apparent clearance and apparent volume of distribution.
- Change from baseline over the course of the study in the following PD parameters: urinary glycolate excretion, plasma oxalate concentration, plasma glycolate concentration and urine oxalate:creatinine ratio
- Quality of life as assessed by Kidney Disease Quality of Life Questionnaire (KDQOL) for adults (≥ 18 years of age) and the PedsQOL (the generic and ESRD modules) for children (< 18 years of age)
- Incidence of ADA

4. PATIENT POPULATION

4.1. Patient Definitions

The populations (analysis sets) are defined as follows:

- Safety Analysis Set: All patients who receive any amount of study drug.
- PD Analysis Set: All patients who receive any amount of study drug and who have at least 1 post-dose urine sample for PD.
- PK Analysis Set: All patients who receive any amount of study drug and who have at least 1 post-dose PK concentration measurement.

The Safety Analysis Set will be used to analyze safety and clinical activity data. The PK and PD Analysis Sets will be used to conduct PK and PD analyses, respectively.

4.2. Protocol Deviations

Protocol deviations will be classified into major or minor deviations by medical review. A major deviation is defined as a deviation that may significantly impact the completeness, accuracy and/or reliability of study data; that may significantly affect a patient's rights, safety and well-being (ICH E3 R1 Structure and Contents of Clinical Study Reports Guidance for Industry, 2013). Deviations not classified as major will be assigned as minor.

Protocol deviations will be summarized in the CSR.

5. GENERAL STATISTICAL METHODS

5.1. General Methods

Continuous data will be described using descriptive statistics such as the number of observations (n), mean, standard deviation, standard error, median, quartiles, minimum, and maximum. For the summary statistics of all numerical variables unless otherwise specified, minimum and maximum will be displayed to the same level of precision as reported. Median and mean will be presented to the level of precision collected in the database plus 1 additional decimal. The standard deviation and standard error will be presented to the level of precision collected in the database plus 2 additional decimals.

For assessments with repeated collections at a given study visit (e.g., ECG parameters, height for patients <18 years of age), the mean will represent the value at the visit for all parameters except for 24-hour urine PD parameters. For 24-hour urine PD parameters, if there are repeated collections at a particular visit then the median will represent the value at that visit. For biomarker and/or laboratory data, if any value is recorded as less than the lower limit of quantification (LLOQ) then the value used for calculations will be assigned a value of LLOQ.

Categorical and ordinal data will be described using the patient count and percentages in each category. When count data are presented, the percentage will not be presented when the count is zero.

Study Day 1 will be defined as the day of the first dose of lumasiran in this study. Study day will be calculated relative to the first dose date of study drug for all patients:

If the assessment date is after the date of first study drug dose, then the study day will be calculated as:

$$\text{Study Day} = \text{Date of assessment} - \text{date of first dose of study drug} + 1,$$

If the assessment date is before the date of the first dose of study drug, then the study day will be calculated as:

$$\text{Study Day} = \text{Date of assessment} - \text{date of first dose of study drug}$$

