- Hatched columns indicate study visits to be conducted **only** for subjects who require monthly dosing.

^a Screening and Baseline visits may be combined, if possible. Assessments required prior to dosing during the screening or baseline visit in this protocol do not need to be repeated if performed in the ALN-GO1-001 protocol within the 30 days before the first dose with the exception of vital signs, ECGs, and physical examinations.

^b Patients who discontinue study drug early will be asked to return for their next scheduled visit to complete ET assessments and to complete safety follow-up visits once every 3 months, per the safety follow-up schedule in this table, for up to 6 months after the last dose of lumasiran (Section 5.3.1).

^c Demographic data will be obtained from Study ALN-GO1-001.

^d Complete medical history will be obtained at screening and any changes will be updated on admission at the Baseline visit, if different from the Screening visit. Events occurring after signing of the informed consent or assent (if applicable) form and before study drug administration will be captured as medical history.

^e During the Baseline visit and at EOT, height will be measured in triplicate for all patients; for all other study visits height will only be measured for patients <18 years of age. For patients <18 years of age, at each time point, height will be measured in centimeters, and in triplicate, to facilitate calculation of eGFR using the Schwartz Bedside formula.

^f Vital signs (blood pressure, heart rate, body temperature, and respiratory rate) will be measured in the supine or seated position after the patient has rested comfortably for approximately 10 minutes. Body temperature can be measured using oral, tympanic, or axillary methods; the temperature measurement method should be consistently utilized for the study duration, if feasible. At Baseline only, vital signs will be measured within 1 hour predose; and 30 minutes (\pm 5 minutes) and 4 hours (\pm 15 minutes) postdose.

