5.3. Baseline Definitions

Baseline will be defined as the derived baseline value in Study ALN-GO1-001 (refer to SAP ALN-GO1-001, Version 2.0; dated August 13, 2018). For data not collected in the parent study (e.g. KDQOL-36, PedsQOL, Renal Ultrasounds), the baseline value will be defined as the latest collection prior to the first dose of lumasiran in this study.

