- ALT or AST >1 and ≤ 3 , ALT or AST >3 and ≤ 5 , ALT or AST >5 and ≤ 10 , ALT or AST >10 and ≤ 20 , AST or ALT $>20 \times$ ULN
- WNL, ALP $>1.5 \times$ ULN
- Total bilirubin >1.5 and ≤ 2 , total bilirubin >2 and ≤ 3 , total bilirubin >3 and ≤ 5 and total bilirubin >5

eDISH plots of peak total bilirubin at any time versus peak ALT or AST at any time will also be presented.

Vital Signs: Descriptive statistics for each vital sign (e.g. systolic blood pressure, diastolic blood pressure, pulse rate, body temperature, respiratory rate, height, weight, body mass index) will be summarized at scheduled visits. Summaries will include actual values and changes from baseline. A summary table of potentially clinically significant shifts in vital signs will also be generated separately for pediatric patients (<18 years old) and adult patients.

For any patient <18 years of age at screening, the modified z-score will be calculated for height, weight and body mass index (BMI) according to the CDC growth chart f. Descriptive statistics of z-scores by visit and treatment arm will be summarized. A tabular summary of the proportion of patients with z-scores at various cut-points (e.g., above and below 2 SD) will also be summarized.

A separate listing of vital sign data will be generated. Per patient plots of z-scores over time for those patients <18 years of age at screening in Study 001 will also be generated.

12-lead ECGs: Electrocardiogram (ECG) parameters include rhythm, ventricular rate, PR interval, QRS duration, QT interval, and QTc interval. Corrected QT interval (QTc), if not collected, will be calculated using the Fridericia's correction formula.

$$\text{Fridericia's cube-root corrected QT: } \text{QTcF (ms)} = \text{QT (ms)} \times \sqrt[3]{\frac{\text{HR(bpm)}}{60}}.$$

The number and percentage of patients with normal, abnormal, and clinically significant abnormal results at baseline and each time point will be summarized.

For electrocardiogram parameters, these will be summarized using descriptive statistics for actual values and for changes from baseline by scheduled time of evaluation.

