Baseline, post baseline maximum QTcF and post baseline maximum change from baseline in QTcF during the study will be summarized with descriptive statistics. The incidence of notable ECG changes from baseline in maximum absolute QTcF, intervals (≤ 450 , > 450 , > 480 , and > 500 ms) over all post-treatment evaluations, as well as in QTcF, maximum changes from baseline (≤ 30 ms, > 30 to 60 ms and > 60 ms) over all post-treatment evaluations will be summarized.

A listing of all ECG data will be provided.

Physical Examinations: During the study, full physical examinations and symptom directed physical examinations will be conducted. If any abnormalities are observed during these physical examinations or worsened from baseline, then this will be recorded on the AE form.

A separate listing per patient will be generated to display the dates and times of the physical examination.

Renal Ultrasounds: During the study, renal ultrasounds will be collected at baseline, Month 12 and Month 24. The number and percentage of patients at baseline with findings of normal, abnormal, not clinically significant, clinically significant will be summarized. In addition, the number and percentage of patients in categories to indicate if a significant change from baseline has been documented will also be summarized at each post-baseline visit. Listings will also be generated.

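### SAP 5.1's visit-mean rule, as written, merges the study's only scheduled postdose vital signs (Day 1) with the predose reading

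*SAP*

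**What the plan says.** **Repeats within a visit.** SAP 5.1 covers assessments collected more than once at a visit and states that "the mean will represent the value at the visit for all parameters except for 24-hour urine PD parameters". ECG parameters and height in patients under 18 are given as examples, not as a closed list. The one exception is 24-hour urine PD parameters, for which "if there are repeated collections at a particular visit then the median will represent the value at that visit".

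**When vital signs are taken.** Protocol Table 1, footnote f, says: "At Baseline only, vital signs will be measured within 1 hour predose; and 30 minutes" and 4 hours postdose. The general notes to Table 1 ask for assessments predose where applicable, so Day 1 is the only visit with scheduled postdose readings.

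**How vital signs are reported.** SAP 7.3.1 gives descriptive statistics at scheduled visits, as actual values and changes from baseline. It adds: "A summary table of potentially clinically significant shifts in vital signs will also be generated separately for pediatric patients" and for adults. It also provides that "A separate listing of vital sign data will be generated". Nothing separates predose from postdose. For ECG parameters, the same section does organise the summary by scheduled time of evaluation.

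**Baseline.** SAP 5.3: "Baseline will be defined as the derived baseline value in Study ALN-GO1-001", with an exception only for data that the parent study did not collect.

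**The concern.** A mean suits true replicates, such as three ECGs five minutes apart or three height measurements, because they estimate the same quantity and averaging removes noise. Predose, 30-minute and 4-hour vital signs are not replicates. They are taken in different exposure states, and averaging them removes the contrast that makes the postdose readings informative.

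The SAP does not exempt timed readings from the rule, and the vital-signs text has no by-time-point instruction that would override it. A programmer who averaged the three sets would be following the plan.

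What is at stake is the tabulated Day 1 vital signs in a study whose primary objective is safety. Enrolment may follow completion of the parent study by up to 12 months (Protocol 5.1), so Day 1 can be a re-exposure after a gap. Protocol 8.2.8 also promises vital signs for each on-study evaluation, which a pooled value does not deliver.

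**Working it through.** The documents give no figure on this point, so there is nothing to reproduce. The check applies the rule to the scheduled collections. The sizes of the changes below are assumed for illustration; the fractions are not.

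**1. Day 1 vital signs.** Let the predose value be P, the 30-minute value P + d1 and the 4-hour value P + d2 (three sets, footnote f).

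Visit value under SAP 5.1 = [P + (P + d1) + (P + d2)] / 3 = P + (d1 + d2)/3.

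| d1 (30 min) | d2 (4 h) | Shift in the visit mean | Largest true shift |
|---|---|---|---|
| 30 | 0 | 30/3 = 10 | 30 |
| 30 | 30 | 60/3 = 20 | 30 |
| 30 | −30 | 0/3 = 0 | 30 |
| −30 | 0 | −30/3 = −10 | 30 |

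A change D at one postdose time therefore shows as D/3, and at both as 2D/3. For example, with assumed systolic readings of 120, 84 and 118, the mean is 322/3 = 107.3. A fall of 36 at 30 minutes appears as a fall of 12.7 (120 − 107.3).

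**2. Effect on change from baseline.** With parent-study baseline B, the Day 1 change is (P − B) + (d1 + d2)/3. The reference B is untouched; only the postdose part of the Day 1 value is diluted.

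**3. Does the same rule distort the QTcF maxima?** Protocol 7.4.4 makes every post-baseline ECG single and predose. The mean of one recording is that recording: 482 ms stays 482 ms. No threshold category changes under the current schedule.

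**4. Does it distort the liver categories?** No scheduled visit has replicate chemistry. Averaging could matter only if two central results carried the same visit label. A value a × ULN would then drop out of the >3 × ULN group when the second is at most 6 − a:
- 4.0 needs a second value of 2.0 or less; 5.0 needs 1.0 or less.
- 3.5 with 2.4 averages 2.95 (lost); 3.5 with 2.6 averages 3.05 (kept).

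A repeat recorded as an unscheduled visit is not averaged, so the 3.5 counts.

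**The case against.** **Timed readings are not repeated collections.** The two examples in SAP 5.1 are planned replicates, and a sensible programmer might keep the three Day 1 sets apart. That is a fair reading of intent. However, the examples are illustrative, the operative words cover all parameters but one group, and SAP 7.3.1 specifies time of evaluation for ECGs while omitting it for vital signs. The text as it stands leads to averaging.

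**The consequence is small.** Only one visit is affected. Individual values are listed, the baseline reference is the parent study's, and safety-relevant findings are to be documented as adverse events (Protocol 7.4.8.2), which are the primary endpoint. All of this stands and limits the impact. It does not restore the postdose contrast in the tables. The protocol also does not say why the postdose readings are taken, so their use for detecting acute effects is an inference.

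**A stronger reading is tempting.** A reader might infer that averaging also biases the QTcF and liver tables toward safety, since SAP 7.3.1 says that "post baseline maximum QTcF and post baseline maximum change from baseline in QTcF during the study will be summarized" and the liver categories are threshold-based. The documents do not support this as a general statement:
- Post-baseline ECGs are single, and the QTcF categories run over all post-treatment evaluations.
- SAP 5.6 counts unscheduled results in categorical worst-value summaries.
- Apart from eGFR, only central laboratory data are summarised, so a local result and its central confirmation are not averaged.
- Liver categories are taken at any post-baseline visit, and eDISH plots use peak values.

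What remains is narrow. The SAP does not say whether averaging comes before or after thresholding if two results share a visit label. Discretionary extra ECGs or repeat laboratory tests could do so, as could any 2-to-4-hour ECGs recorded before Amendment 2 removed that time point.

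**Conclusion.** The point holds for Day 1 vital signs. As written, SAP 5.1 and 7.3.1 together reduce a postdose change to one third of its size if it appears at one time point, to two thirds if at both, and to nothing if equal and opposite. These fractions assume that all three sets are recorded under one visit label and that the rule is applied literally. Whether anyone would be missed in the potentially clinically significant shift table cannot be sized: the SAP gives no cut-offs for it and does not say whether it uses individual readings or visit values. With at most 20 patients planned, one patient is at least 1/20 = 5% of the total.

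The parent-study baseline and the listings are unaffected. The inference that the QTcF and liver tables are generally biased toward safety is not supported. For those tables, only the handling of two results under one visit label needs a clarifying sentence.

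**What to change.** 1. In SAP 5.1, limit the mean to planned replicates, naming the triplicate Baseline ECG and triplicate height. Leave the median rule for 24-hour urine PD parameters as it is.
2. In SAP 7.3.1, summarise Day 1 vital signs by time point: predose, 30 minutes and 4 hours. Change from the Day 1 predose value could be added as a supplementary column, labelled so that it is not confused with the parent-study baseline of SAP 5.3.
3. As a minor clarification, state that maximum, shift and threshold summaries use each individual post-baseline result when two results share a visit label.

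The cost is a few sentences in the SAP and one extra vital-signs table. No new data are needed, because the three sets are already scheduled.

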5.2. Computing Environment

All statistical analyses will be performed using validated SAS statistical software Version 9.4 (or later), unless otherwise noted.

5.3. Baseline Definitions

Baseline will be defined as the derived baseline value in Study ALN-GO1-001 (refer to SAP ALN-GO1-001, Version 2.0; dated August 13, 2018). For data not collected in the parent study (e.g. KDQOL-36, PedsQOL, Renal Ultrasounds), the baseline value will be defined as the latest collection prior to the first dose of lumasiran in this study.

5.4. Dose Groups

All tables and figures will be presented by the initial dose regimens in this study, unless otherwise specified:

- 1 mg/kg once monthly
- 3 mg/kg once every 3 months
- Pooling of 1 mg/kg once monthly or 3 mg/kg once every 3 months
- 3 mg/kg once monthly
- Total

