6.5. Dosing and Extent of Exposure

Summaries of exposure will include the following categories such as, but not limited to: total number of doses received per patient, mean number of doses per patient, cumulative number of doses received per study group, duration of drug exposure (months) per study group, cumulative drug exposure time (months) per study group, the total dose administered (mg) and total volume administered (mL).

Definition of drug exposure (days) will be defined as the minimum of [Exposure time= (date of last exposure – date of first dose +1)] where date of last exposure will represent either the date of the last dose administered dose +84, analysis cut-off date or end of study date.

Dose interruptions and compliance are not taken into account.

A separate per-patient exposure listing will be generated to display the initial dosing regimen in the parent study (ALN-GO1-001), the initial dosing regimen in this study and changes to the dose and/or regimen during this study.

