7. STATISTICAL ANALYSIS

7.1. Primary Endpoint

7.1.1. Evaluate the incidence of Adverse Events (AEs)

The primary safety parameter is the assessment of treatment-emergent AEs which will be defined as an AE that occurs or worsens on or after the first lumasiran dose date/time of this study though 84 days after the last dose of study drug. In addition, any AE that worsens in intensity or was subsequently considered related to study drug will be considered treatment-emergent. All analyses of AEs will be performed on the Safety Analysis Set.

For summaries of AEs, there will be 3 sets of summaries: all AEs, AEs classified as renal stone events and AEs excluding those classified as renal stone events. A medical review of all AEs will be conducted to identify renal stone events.

AEs will be coded using the MedDRA coding system (version 21.0 or later) and displayed in tables and data listings by SOC and PT. Patients who report multiple occurrences of the same PT will be classified according to the most related or most severe category. Patients with a missing relationship to study drug will be classified as the most related category. Drug related AEs include events considered definitely related or possibly related to study drug by the investigator or events with missing relationship.

An overview table of AEs will be tabulated. The overview table will include the number and percentage of patients in following categories such as, but not limited to:

- At least 1 AE
 - At least 1 drug related AE
- At least 1 severe AE
 - At least 1 drug related severe AE
- At least 1 serious adverse event (SAE)
 - At least 1 drug related SAE
- At least 1 AE leading to treatment discontinuation
 - At least 1 drug related AE leading to treatment discontinuation
- At least 1 AE leading to study withdrawal
 - At least 1 drug related AE leading to study withdrawal
- Death

Tabulations by SOC and PT displaying the number of patients (percentage) and total events will be produced for the following tables:

- All AEs
- Serious AEs
- AEs by maximum severity

- AEs related to treatment
- AEs and SAEs related to treatment by maximum severity

There will also be an all AE table generated displaying rates of AEs adjusted for exposure-time.

Separate listings will be provided for deaths, SAEs, and AEs leading to discontinuation of study drug, dose interruption, or study withdrawal. By-patient AE listings will be provided.

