A subset of key AE outputs will also be generated to compare study groups of patients initially dosed with 3 mg/kg once monthly versus 3 mg/kg once every 3 months of lumasiran.

Tabulations of the AE data will be adjusted for exposure-time.

Summaries of other Standardised MedDRA Queries (SMQs) or AE groupings may be summarized such as but not limited to the following:

Injection Site Reactions [ISRs]: AEs mapping to the HLT="Injection Site Reactions" using MedDRA dictionary will be included in the summary. Frequency (percentages) of ISRs by HLT and PT will be generated. A separate listing will be generated to display all patients who reported ISRs.

A table will also be generated to display the number of patients with at least 1 ISR, total number of injections, total number of injections complicated by ISRs and corresponding % of injections complicated by ISR with the most common signs and symptoms reported due to ISRs. If there are multiple ISRs that occur in between 2 consecutive injections, then these events will be considered as 1 ISR and considered related to the preceding injection.

Hepatic AEs, including AEs of liver function test (LFT) abnormalities: AEs mapping to the SMQ drug-related hepatic disorders - comprehensive search (includes all narrow and broad terms). Frequency (percentages) of drug-related hepatic disorders will be summarized by SOC and PT. A separate listing will be generated of all patients reporting these events.

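### If patients on 3 mg/kg monthly or 3 mg/kg every 3 months switch after first dose and AE rates differ by regimen, the exposure-adjusted AE comparison describes starting regimens, not rates on each regimen

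*SAP*

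**What the plan says.** **Grouping.** SAP 5.4 sets the default: "All tables and figures will be presented by the initial dose regimens in this study, unless otherwise specified". The groups are 1 mg/kg monthly, 3 mg/kg every 3 months, these two pooled, 3 mg/kg monthly, and Total.

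**The comparison.** SAP 7.1.1 plans a subset of key AE outputs to "compare study groups of patients initially dosed with 3 mg/kg once monthly versus 3 mg/kg once every 3 months of lumasiran", followed by "Tabulations of the AE data will be adjusted for exposure-time". The same section says of the overall AE display: "There will also be an all AE table generated displaying rates of AEs adjusted for exposure-time".

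**Exposure.** In SAP 6.5 the span starts at first dose and ends at the earliest of three dates, "where date of last exposure will represent either the date of the last dose administered dose +84" days, the analysis cut-off or the end of study. It adds: "Dose interruptions and compliance are not taken into account". The treatment-emergent definition in SAP 7.1.1 likewise runs from first dose in this study through 84 days after the last dose, whatever the regimen at onset.

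**Regimen changes.** SAP 2.1 lets patients change regimen at any time, on emerging data and with SRC approval. Protocol 4.1 and 6.2.2 allow SRC-authorized changes for one patient or a whole cohort, capped at the highest dose evaluated in the parent study. A change may also apply to the starting regimen of patients not yet dosed here. In the SAP text available for this review, changes appear only in the SAP 6.5 per-patient listing of the initial regimens and "changes to the dose and/or regimen during this study".

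**The concern.** An exposure-adjusted rate under a regimen label invites reading as the rate of events while on that regimen. Under the SAP rules it is that only while patients stay where they started. After a switch, later events and later person-time remain in the starting column.

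This is the only head-to-head regimen comparison named in the available SAP text. Switching is an anticipated feature of the design, and treatment may last up to 54 months, so an early change could put most of a patient's person-time on another regimen. The SAP plans to list the changes but carries them into no AE summary. A reader asking whether monthly dosing has a different AE rate from dosing every 3 months would have to match the listings by hand, and would still lack person-time on each regimen.

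Switches by 1 mg/kg monthly starters affect only their own column and the pooled one, not the two compared groups.

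**Working it through.** The plan gives no AE rate, switch count or switch date and no power calculation, so there is no stated figure to reproduce. The check has two parts: what the rules do to a switcher, and an illustration of possible size.

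**1. What the rules do to a switcher.** Take a patient who starts on 3 mg/kg monthly and moves to every 3 months at month 12.
- Group: 3 mg/kg monthly throughout (SAP 5.4, 7.1.1).
- Person-time: one span from first dose, not cut at month 12 (SAP 6.5).
- Events: every treatment-emergent AE in that span, including those after month 12 (SAP 7.1.1).

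Numerator and denominator therefore both stay in the monthly column. A change made before the first dose in this study is different: SAP 5.4 groups by initial regimen in this study, so that patient is already classified correctly.

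**2. Maximum span.** Protocol Table 1 puts end of treatment at Day 1428. Adding 84 days gives Day 1512, a span of 1512 days, and 1512/28 = 54 months of 28 days.

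**3. Illustration.** Assumptions: constant rates, 54 months' follow-up for everyone, an every-3-months rate of 1 and a monthly rate of R. All monthly starters move to every 3 months at month m, and no one in the other group moves.

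Tabulated ratio = [m × R + (54 − m) × 1] / 54

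For R = 2:
- m = 6: (12 + 48)/54 = 1.11
- m = 12: (24 + 42)/54 = 1.22
- m = 24: (48 + 30)/54 = 1.44
- m = 36: (72 + 18)/54 = 1.67

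For other assumed values of R:

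| True ratio R | m = 6 | m = 12 | m = 24 | m = 36 | No switch |
|---|---|---|---|---|---|
| 1 | 1.00 | 1.00 | 1.00 | 1.00 | 1.00 |
| 1.5 | 1.06 | 1.11 | 1.22 | 1.33 | 1.50 |
| 2 | 1.11 | 1.22 | 1.44 | 1.67 | 2.00 |
| 3 | 1.22 | 1.44 | 1.89 | 2.33 | 3.00 |

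If only a share p of monthly starters moves at month 12 and R = 2, the ratio is 2 − p × (42/54): 1.81 for p = 0.25 and 1.61 for p = 0.5.

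**4. Direction is not fixed.** Suppose instead that all every-3-months starters move to 1 mg/kg monthly at month 12, with R = 2 and a rate r on 1 mg/kg monthly. The ratio is 2 / [(12 + 42r)/54]:
- r = 0.5: 2/0.611 = 3.27
- r = 1: 2/1 = 2.00
- r = 1.5: 2/1.389 = 1.44

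The tabulated ratio can therefore lie above or below the on-regimen ratio.

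**The case against.** The strongest answer is that the SAP does not claim what is being missed. The outputs are labelled by initial regimen and compare patients initially dosed with each one. That is a legitimate summary, it is descriptive, and no more than 20 patients are planned. This stands: the planned tables are not wrong and should stay.

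It can also be said that the material to resolve the matter is already planned. The exposure listing shows each regimen change, the by-patient AE listings show each event, and SAP 1 allows further exploratory analyses. With so few patients, matching them is feasible. This stands in part. Listings permit reconstruction but give no on-regimen denominators or rates, and an analysis that is permitted but not named would be chosen after the data are seen.

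A third answer is that a table by regimen at onset is not clean either. Attribution would change at once at a switch, while the SAP treats events up to 84 days after the last dose as treatment-emergent. Regimen would also be mixed up with time on study and with the reason for switching. This stands too, and it is why such a table can only supplement the planned one.

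Some stronger readings are tempting but unsupported:
- *The primary endpoint is compromised.* Moving events between regimen columns does not change the Total column.
- *Patients may switch freely throughout.* The at-any-time wording is in SAP 2.1 only and is tied to SRC approval. Protocol 4.1 and 6.2.2 require SRC authorization and set a dose cap.
- *Switching alone biases the comparison.* AE rates must also differ between the regimens involved.
- *The SAP contains no such summary anywhere.* The text of SAP Section 8, Changes to Planned Analyses, was not available, so absence is claimed only for the rest of the SAP.

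**Conclusion.** The point holds as a conditional one, at the level of an improvement to consider. If patients in either compared group change regimen after their first dose in this study, and AE rates differ between the regimens involved, the exposure-adjusted comparison cannot be read as rates on each regimen.

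The documents do not allow the size or direction to be stated. The ratios above rest on assumed rates, constant over time, and on assumed switch patterns. They show that the effect could be large if switching is early and widespread, not that it will be. With no switches in the compared groups there is nothing to correct. Confidence is medium, because switching is allowed but its frequency is not given and Section 8 could not be checked. The point concerns AE outputs only, and no change to the PD tables is proposed.

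**What to change.** Keep all initial-regimen tables as planned. Add to SAP 7.1.1 that, if any patient switches regimen after the first dose in this study, one supplementary descriptive AE and injection site reaction (ISR) table with exposure-adjusted rates will be produced. It should:
- assign each event and each day of person-time to the regimen of the most recent dose. This extends a rule the SAP already has: multiple ISRs between two injections are "considered as 1 ISR and considered related to the preceding injection";
- carry a row for events whose regimen cannot be determined, since SAP 5.5 assigns no date to AEs with missing or partial dates;
- state in advance how events in the 84 days after a switch are handled, for example kept with the most recent dose, with an optional version that sets that period aside. The 84 days would be a convention borrowed from the SAP's follow-up window, not an estimate of carry-over.

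The cost is low: one derived variable and one conditional table, because the change dates are already needed for the SAP 6.5 listing. The downsides should be footnoted. Switchers appear in more than one column, so column counts will not sum to the total. Regimen is confounded with time on study and with the reason for switching. Rates will be imprecise with at most 20 patients.
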